Annex 1: Study evaluations

Annex 2: Information sheet for subjects (presented in a separate document)

Annex 3: Informed consent form (presented in a separate document)

Appendix 1

STUDY EVALUATION SCHEME

Procedure \ Visit	V0	V1
Sign informed consent		x (in patients who are still being monitored at their center)
Inclusion/exclusion criteria	x	
Retrospective collection of variables	x	
Collection of anthropometric and sociodemographic variables	x	
Collection of laboratory variables	x	
Collection of post-surgical clinical evolution variables	x

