ethical considerations	Informed consent will be obtained from patients who are currently being followed up at the reference centers.
Funding source	Not precise

2. THEORETICAL FRAMEWORK. PROBLEM STATEMENT:

Background

Obesity affects approximately 45-55% of patients with schizophrenia (1). Weight gain in these patients may be due to different factors such as the use of antipsychotic drugs with an unfavorable metabolic profile, the coexistence of sleep disorders or negative cognitive symptoms that often translate into a more sedentary lifestyle and alterations in eating behavior, among others (2). The coexistence of obesity and its comorbidities in this group of patients significantly worsens both their physical and mental health (3). In fact, cardiovascular disease is one of the main causes of mortality in patients with schizophrenia (4).

Lifestyle interventions, while they may be effective in people with schizophrenia (5), often fall short of achieving weight goals. At present, obesity surgery represents the most effective treatment in terms of weight loss and resolution of comorbidities, being indicated in cases of patients with a body mass index (BMI) > 35 kg/m² with comorbidities or BMI > 40 Kg/m² with/without comorbidities. However, the access of patients with schizophrenia to bariatric surgery techniques is usually limited by different factors such as fear of a possible worsening of the underlying disease, or a lower weight loss in this population, among others. In addition, clinical practice guidelines recommend that all patients with psychiatric pathologies be evaluated in a regulated manner prior to surgery (6), although the content of this evaluation and the criteria for declining or accepting surgery are not clear. Although the course of schizophrenia is variable and its symptoms may be stable without being a clear contraindication for bariatric surgery, in actual practice, a considerable number of professionals contraindicate bariatric surgery in the presence of a psychotic disorder (7).

For these reasons, data on the efficacy of bariatric surgery in patients with schizophrenia are scarce and limited to very small case series with short-term follow-up (2,8,9). Our objective is therefore to carry out a multicenter retrospective study that allows us to study the long-term evolution after bariatric surgery in a large series of patients, focusing not only on weight evolution but also on the long-term evolution of psychiatric pathology.

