It is the responsibility of the investigator to obtain the informed consent of the patient. The patient will not be able to participate in any study-specific procedure without obtaining their consent, or that of their legal guardian/family member when the patient is unable to give consent due to their clinical situation.

Before including any subject in the study and before obtaining informed consent, the investigator or the person designated by the investigator will explain to the potential participating subject or their legal guardian/family member the objectives, methods, and potential risks of the study and any inconvenience it may cause. The explanation about the nature, scope and possible consequences of the study will be made in an understandable language.

The prospective participant or their legal guardian/family member should have time to consider their decision to participate in the study, and have the opportunity to ask questions. After this explanation, and before entering the study, the consent must be properly recorded by the signature of the subject or their legal guardian/family member. Given the retrospective nature of the study, it is likely that some patients to be included have died or are no longer seen at their referral center. In this case, informed consent will not be obtained, but the research team undertakes to verify that there is no record of the subjects' express opposition in the clinical history and to comply with the confidentiality regulations.

In addition, since the use of pseudonymized personal data for biomedical research purposes requires technical and functional separation between the research team, and those who perform the pseudonymization and keep the information that enables re-identification, the person who performs the pseudonymization for this study does not will be part of the research team.

For access to the pseudonymous data, an express commitment of confidentiality and not to carry out any re-identification activity is sent, and that specific security measures will be adopted to avoid re-identification and access by unauthorized third parties.

The Model Patient Information Sheet and the Consent Form are presented as an Annex.

Considerations on the treatment of biological samples

Does not apply

Data confidentiality

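### Appendix 1 places consent after outcome collection, against section 6, and asking only patients still followed lets refusals raise the observed loss and death proportions

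*Protocol*

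**What the plan says.** **Order of consent.** The study evaluation scheme in Appendix 1 has two columns, V0 and V1. Eligibility, the row "Retrospective collection of variables", and the anthropometric, laboratory and post-surgical evolution rows are all marked under V0. Consent is the only row marked under V1, where the cell reads "x (in patients who are still being monitored at their center".

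Section 6 (Ethical aspects, informed consent) says: "After this explanation, and before entering the study, the consent must be properly recorded by the signature". It also says: "The patient will not be able to participate in any study-specific procedure without obtaining their consent".

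**Who is asked.** The synopsis states: "Informed consent will be obtained from patients who are currently being followed up at the reference centers". For patients who have died or no longer attend their centre, section 6 says: "In this case, informed consent will not be obtained". The team must instead check that there is no "express opposition in the clinical history".

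**Why attendance matters here.** Section 4 lists loss to follow-up, death and adherence to scheduled visits among the secondary variables. It aims to include all cases detected in Spain, expects at least 10, and sets four controls per case.

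**The concern.** There are two separate problems.

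The first is a contradiction. If centres follow Appendix 1, post-surgical outcomes are recorded before the patient is asked. If they follow section 6, they are not. The synopsis lists many centres, and different centres could follow different passages. The protocol gives no rule for data already collected when a patient then refuses.

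The second is an asymmetry that follows from the consent rule itself. Patients no longer seen, or dead, enter without being asked. Patients still followed enter only if they agree. A refusal on request therefore takes a living, attending patient out of the denominator and leaves the lost and dead patients in it. Loss to follow-up and death are reported variables, so their observed proportions rise. If patients with schizophrenia and controls refuse at different rates, the rise is unequal and appears as a group difference. The protocol does not provide for counting refusals, and its limitations section names only the retrospective nature, so a reader of the results could not judge the effect.

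**Working it through.** The protocol gives no refusal rate or loss rate, so there is no figure of its own to reproduce. The check is a comparison of passages followed by an illustration on assumed rates.

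**1. Passages side by side.**

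| Item | Appendix 1 | Section 6 |
|---|---|---|
| Outcome variables | V0 | Not before consent, for patients who are asked |
| Signed consent | V1, patients still monitored | Before entry and before any study-specific procedure |
| Died or no longer seen | No consent mark | Included unless opposition is on record |

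If V1 follows V0, the first two rows cannot both be followed. The third row is consistent and gives the asymmetry.

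**2. Effect on the observed loss proportion.** Let *l* be the true proportion lost and *r* the refusal rate among patients still followed. Assume for simplicity that everyone not lost is asked and that lost patients all enter. Then

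observed loss = *l* / [*l* + (1 − *l*)(1 − *r*)].

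Assumed: *l* = 0.30 in both groups.

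| Refusal, cases vs controls | Cases | Controls | False gap |
|---|---|---|---|
| 20% vs 5% | 0.30/(0.30 + 0.70 × 0.80) = 34.9% | 0.30/(0.30 + 0.70 × 0.95) = 31.1% | 3.8 points |
| 30% vs 10% | 0.30/(0.30 + 0.70 × 0.70) = 38.0% | 0.30/(0.30 + 0.70 × 0.90) = 32.3% | 5.7 points |
| 20% vs 20% | 34.9% | 34.9% | 0 |

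The last line shows that equal refusal with equal loss produces no false gap, although both proportions are still overstated by 4.9 points. The same formula applies to death, with the true death proportion in place of *l*.

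**3. What the formula does not contain.** It has no term for the time of consent. The same gaps arise whether consent is signed before or after extraction.

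**4. Small numbers.** At the stated minimum of 10 cases with an assumed 3 lost, one refusing attender moves observed loss from 3/10 = 30% to 3/9 = 33%. A gap of 4 to 6 points on 10 cases is about half a patient.

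**5. Weight outcomes.** Let *a* be the share of patients attending. After refusals, the attending share is *a*(1 − *r*)/(1 − *ar*). With assumed *a* from 0.5 to 0.9 and *r* from 0.1 to 0.3, that share falls by between 0.010 (*a* = 0.9, *r* = 0.1: 0.81/0.91 = 0.890) and 0.088 (*a* = 0.5, *r* = 0.3: 0.35/0.85 = 0.412). If attenders differ from the rest by an assumed 5 points of total weight loss, the group mean shifts by 5 × 0.010 = 0.05 to 5 × 0.088 = 0.44 points. The effect on the main outcome is therefore small under these assumptions.

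**6. Effect of the proposed denominator.** Counting refusers as still followed gives 0.30/(0.30 + 0.70 × 0.80 + 0.70 × 0.20) = 0.30/1.00 = 30%, the true value, whatever the refusal rate.

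**The case against.** The strongest reply is that this is a clerical slip in an annex. V0 and V1 are not defined, the study is a chart review without study visits, and V0 could simply label record review and V1 patient contact. The work plan in section 5 does not place consent after collection, and section 6 is explicit. This stands in part: the order rests on the usual meaning of the labels. It is also a reason to correct the scheme, since nothing in Appendix 1 tells a centre to read it otherwise.

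Several further objections stand and limit the point.

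- A reader might infer that only attending patients can refuse. The documents do not support this: recorded express opposition also excludes patients who are not asked. What holds is that only patients still followed are actively asked.
- A reader might infer that inclusion will depend on known outcomes. No rule says so. In a chart review the outcomes already exist, and treating staff may know them whenever consent is signed, so reordering alone would not remove that risk.
- A reader might take the 4 to 6 points as the cost of the wrong order. They are not; they illustrate unequal refusal, and every input is assumed. The documents give no reason to expect more refusal among cases.
- The formula treats patients not asked as the same people as patients lost. A patient who completed the 5 years and was then discharged is not lost, yet is not asked. If only a fraction *s* of those not lost are still followed, *r* becomes *s* × *r* and the gap shrinks.
- Requiring consent before any data extraction would be too strict, because identification and matching on age, sex, BMI and type of surgery need record access first.

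The information sheet and consent form are separate documents not shown here and may say what happens to data after refusal. Denominators may be set in an analysis plan, also not shown. Neither would settle the conflict of order within the protocol.

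**Conclusion.** The contradiction between Appendix 1 and section 6 holds on the ordinary reading of V0 and V1, needs no assumed figure, and must be reconciled. The asymmetry also holds, because it follows from a stated rule: asking only patients still followed means that refusals on request remove living attenders and can raise the observed loss and death proportions.

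The size cannot be derived from the documents. About 4 to 6 points of false difference in loss is an illustration resting on 30% true loss in both groups, refusal of 20% vs 5% or 30% vs 10%, and everyone not lost being asked. It is zero if refusal and loss are equal in both groups. It concerns secondary variables; a material effect on the weight outcomes is not shown. The point merits correction because the remedy is cheap, not because a large bias has been demonstrated.

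**What to change.** - **Reconcile Appendix 1 with section 6.** Define V0 and V1. For patients still followed, place consent after eligibility and matching but before outcome variables are extracted. State what happens to data already held on a patient who refuses.
- **Count refusals.** Keep an anonymous count, separately for cases and controls, of patients eligible, consented, refused and not asked.
- **Set the denominator.** Report loss to follow-up and death with all eligible patients as denominator, counting refusers as alive and still followed, alongside the figures that leave refusers out.
- **Replace refusing controls early.** When a control refuses, choose another matched control before any outcomes of the replacement are extracted.

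The cost is a correction to one annex, a small count log at each centre and slightly more reporting. No extra patients or procedures are needed. The reordering settles the contradiction; the count and the denominator deal with the asymmetry, which reordering would leave in place.
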